#### **6.3.3. Exclusion criteria**

- Patients that were participating in a clinical trial during the study reference period.
- Patients that, according to investigator's criteria is not capable to understand and fill in the study questionnaires or to give written informed consent

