## 2. List of abbreviations

Abbreviation	Description
ADR	Adverse Drug Reaction
AE	Adverse event
AEMPS	Agencia Española del Medicamento y Productos Sanitarios
AR	Adverse Reaction
CD	Crohn's Disease
CDAI	Crohn's Disease Activity Index
eCRF	Electronic Case Report Form
EQ-5D	EuroQoL Questionnaire
HBI	Harvey-Bradshaw Index
HRQoL	Health Related Quality of Life
IBD	Inflammatory Bowel Disease
PMS	Partial Mayo Score
SAP	Statistical Analysis Plan
SAE	Serious Adverse Event
SIBDQ	Short Inflammatory Bowel Disease Questionnaire
UC	Ulcerative Colitis
UCDAI	Ulcerative Colitis Disease Activity Index

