#### **6.3.2. Inclusion criteria**

- Adult patients (aged  $\geq 18$ )
- Patients diagnosed with UC or CD according to the "World Gastroenterology Organization Practice Guidelines for the Diagnosis and Management of IBD in 2010"
- Patients naive to biologics that started treatment with biologics between June 2011 and June 2013
- Patients in whose biological treatment was prescribed according to daily clinical practice.
- Patients that gave written informed consent

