#### 6.4.4. Study variables

The following **sociodemographic variables** will be collected from patients' medical records or directly from patients during the study visit, straight after their inclusion in the study:

- Age
- Gender
- Race (caucasian, asiatic, latin, black, other)
- Level of education (uneducated, primary education, secondary education, university education)
- Working status (student, self-employed, employed by other, retired, housework, unemployed, temporarily unable to work, permanently unable to work, other)
- Smoking habits (non-smoker, ex-smoker, smoker, number of cigarettes per day)
- Alcohol intake (units per week).

The following **clinical variables** will be collected from patients' medical records (when available) or directly from patients during the study visit, straight after their inclusion in the study:

- Date of diagnosis (UD or CD).
- Disease activity at the beginning of the reference period and at the study visit through collection of the following variables:
  - For UC patients:
    - Partial Mayo Score (PMS) (9 point scale that excludes the endoscopic appearance of the mucosa)
    - General disease activity:
      - Mild: up to four bloody stools daily and no systemic toxicity
      - Moderate: four to six bloody stools daily and minimal toxicity
      - Severe: more than six bloody stools daily and signs of toxicity, such as fever, tachycardia, anaemia, raised erythrocyte sedimentation rate.
      - Fulminant: More than ten bloody stools daily, continuous bleeding, anaemia requiring blood transfusion, abdominal tenderness and colonic dilatation on plain abdominal radiographs.
    - Disease anatomic extent: proctitis, left-sided colitis or pancolitis.
    - Endoscopy findings:

- Normal or inactive disease
- Mild disease (erythema, decreased vascular pattern, mild friability)
- Moderate disease (marked erythema, lack of vascular pattern, friability erosions)
- Severe disease (spontaneous bleeding, ulceration).
- For CD patients:
  - Harvey-Bradshaw Index (HBI) (a simplified version of CDAI)
  - General disease activity:
    - Mild to moderate: ambulatory patients able to tolerate oral alimentation without manifestations of dehydration, toxicity, abdominal tenderness, painful mass, obstruction or >10% weight loss.

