#### 6.4.5. Main outcome

Non responders will be those patients not achieving a reduction in HBI of at least 2 points from baseline for CD, and a decrease in the PMS of at least 2 points for UC.. In the cases where these indexes are not available, clinical response will be evaluated according to physician criteria at short term (10 weeks after starting the anti-TNF) and at long term (at least 6 months after starting the anti-TNF). Primary non-responders (PNR) were defined as patients with no clinical response at short term. Loss of response (LOR) was defined as loss of the effect of the drug along the follow up in a patient with initial response.

Reasons to stop the drug will be classified as follows: PNR, LOR, side effects (SE), remission and other.

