The SSL technology implemented guarantees that all data transferred to the CRO database server will be encrypted and protected from external attacks. An audit trail process will ensure control of every movement made to the data stored. Information registered for every value stored in the database includes: the event date, responsible party, variable, old value, new value, and the type of action taken (creation, updating or deleting). This audit process provides an additional security mechanism for stored data and may also be useful in answering data entry questions by site personnel.

The two questionnaires to be filled in by patients during the study visit will be sent to investigators together with all the study documents. Investigators will have to send all questionnaires completed by included patients at their site to the CRO.

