### 9.2. Monitoring and quality of data

On-site monitoring will not be conducted in the context of this study. Regular fortnightly phone calls will be made by study monitors in order to check inclusion status, solve any potential recruitment issues, check data plausibility etc. Investigators will receive all documents before the study begins. The CRO will provide instructions to investigators on how to introduce data in the eCRF when data collection starts; these instructions will also be briefly reminded to investigators every time they access the eCRF. During the

entire duration of the study, The CRO will provide technical support to investigators participating in the study.

Each investigator will be responsible for ensuring the accuracy of data entered in the eCRF as well as for completing all sections included in the eCRF. Each investigator commits to enter all data following their usual clinical practice.

The CRO will be responsible for supervising patients' recruitment through eCRF. During data collection period, standard monthly emails will be sent to investigators to inform about its progression, deal with any issues and remind investigators on their responsibilities. The CRO will guarantee database quality, compliance and accuracy of data introduced in the eCRF. The CRO will review the information entered through the web application weekly to guarantee data is being introduced correctly. If an inconsistency is detected during eCRF data review, the CRO will contact investigators via fax or email so that information can be clarified.

Investigators will guard original documents from each patient. All the information introduced in the eCRF will need to be traceable from original medical charts. Participating investigators from each site will keep a patient tracking sheet that will contain patients name together with assigned consecutive numbers and date of birth to allow identification. Investigators must also keep the original signed written informed consent from all patients included in the study.

When the CRO receives the completed questionnaires they will be handed to data entry department personnel that will introduce questionnaire answers in the study data base. Patients' questionnaires will be kept in the CRO office until statistical final report is completed. After that, they will be kept by the study sponsor.

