7.2. Primary efficacy endpoint

- **Primary endpoint:** Evaluate the impact of the co-morbidities profile in IBD patients on treatment response to biological therapy.

The analysis that will be performed to answer the objective will be the following:

In order to determine the level of correlation between the co-morbidities profile and treatment response, adjusting for sociodemographic and clinical profile of patients, two logistic regression models will be conducted. The dependent variable of the models will be the **lack of response during the induction phase and the loss of response during the maintenance phase**. In both models independent variables will include all comorbidities, as well as sociodemographic and clinical variables as covariates.

- The following potential variables will be considered for the analysis:
 - Crohn's Disease or Ulcerative Colitis.
 - Myocardial Infarction (yes/no).
 - Congestive Heart Failure (yes/no).
 - Peripheral Vascular Disease (yes/no).
 - Cerebrovascular Disease (yes/no).
 - Dementia (yes/no).
 - Chronic Obstructive Pulmonary Disease (yes/no).
 - Connective Tissue Disease (yes/no).
 - Peptic Ulcer Disease (yes/no).
 - Mild Chronic Hepatopathy (yes/no).
 - Diabetes Mellitus (yes/no).
 - Hemiplegic (yes/no).
 - Moderate-Severe Chronic Kidney Disease (yes/no).
 - Diabetes with lesions in target organs (yes/no).
 - Solid Tumor (yes/no).
 - Leukemia (yes/no).
 - Lymphoma (yes/no).

- Moderate-Severe Chronic Hepatopathy (yes/no).
 - Solid tumor with metastases (yes/no)
 - Acquired immunodeficiency syndrome (AIDS) (yes/no).
 - Gender.
 - Race (caucasian, asiatic, latin, black, other).
 - Level of education (uneducated, primary education, secondary education, university education).
 - Working status (student, self-employed, employed by other, retired, housework, unemployed, temporarily unable to work, permanently unable to work, other).
 - Smoking habits (non-smoker, ex-smoker and smoker).
 - Alcohol abuse (yes/no).
 - Time from diagnostic of disease.
 - Disease location.
 - Discontinuation the biological treatment (yes/no)
- Each one of the variables will be compared between the subjects with primary non-response vs primary response and primary response maintenance vs loss of response and those variables whose p-value is lower than 0.1 are considered potential variables for performing a logistic regression analysis.

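### The exclusion of patients who cannot fill in the study questionnaires serves no stated analysis and can remove consenting patients with co-morbidities under study; the likely loss is very small

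*Protocol*

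**What the plan says.** Protocol 6.3.3, repeated in SAP 3.8, excludes a patient who by the investigator's criteria "is not capable to understand and fill in the study questionnaires or to give written informed consent". The two conditions are joined by an or, so failing either one is enough. Consent is also a separate inclusion criterion in protocol 6.3.2: "Patients that gave written informed consent".

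Two places in the protocol treat the questionnaires as real. Section 8 states: "The two questionnaires to be filled in by patients during the study visit will be sent to investigators together with all the study documents". Section 9.2 says of the completed forms that "they will be handed to data entry department personnel that will introduce questionnaire answers in the study data base". Neither names them. The abbreviation list defines EQ-5D and "Short Inflammatory Bowel Disease Questionnaire" (SIBDQ), and neither instrument appears again.

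The study data come from elsewhere. Under protocol 6.4.4 the clinical variables "will be collected from patients' medical records (when available) or directly from patients during the study visit", and section 6.1 gives the chart priority where the two disagree. Response is defined by change in HBI or PMS. The fallback in protocol 6.4.5 is clinical judgement: "In the cases where these indexes are not available, clinical response will be evaluated according to physician criteria at short term".

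**The concern.** An eligibility rule should protect something the study needs. Here the consent part does so, but the questionnaire part protects data that no stated analysis uses. It also acts on a likely consequence of the exposure. Stroke, hemiplegia and mild dementia can leave a person able to agree to take part but unable to complete a form, and these conditions are among those whose frequency and impact the study sets out to measure.

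This sits badly with the protocol's own aims. Section 4 criticises randomised trials for patient profiles that are too restrictive on co-morbidity, and sections 3.10 and 6.3.1 rely on consecutive recruitment to avoid selection bias. Any loss would also go unreported: the flowchart in SAP 4.2 covers included patients, and no table counts those turned away or the reason.

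**Working it through.** **1. The plan's own figure.** Protocol 7.1 assumes 10 events per variable, at most 10 variables and 50% non-response. N = 10 × 10 / 0.50 = 200 per disease. This matches the stated 200 UC and 200 CD patients, and also 25 sites × 8 patients = 200. Eligibility wording does not enter the formula, so removing the clause leaves the sample size unchanged.

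**2. Search for any use of a questionnaire.**

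| Place | Patient questionnaire? |
|---|---|
| Objectives (protocol 5.1, 5.2; SAP 3.5) | none |
| Variables (protocol 6.4.4) | none |
| Outcome (protocol 6.4.5; SAP 7.1) | none: HBI, PMS or physician judgement |
| Analyses (protocol 7.1 to 7.6; SAP 5 to 7) | none |
| Table index (SAP Appendix 1) | none |
| Data handling (protocol 8, 9.2) | two, unnamed |
| Abbreviations (protocol 2) | EQ-5D and SIBDQ, not used elsewhere |

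**3. Overlap with the exposures.** SAP 7.2 lists 19 co-morbidity terms for the primary models. Three of them (cerebrovascular disease, dementia, hemiplegia) can plausibly prevent form completion. The same three are in the prevalence objective (protocol 7.5; SAP 7.3).

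**4. Size, by illustration only.** The documents give no prevalence and no exclusion rate. Let p be the assumed proportion carrying such a condition among 400 patients who would enter if only the consent rule applied. Let s be the assumed share of those carriers turned away for the questionnaire alone.

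- Carriers = 400p
- Patients lost = 400ps
- Observed prevalence = p(1 − s) / (1 − ps)

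| p | s | Carriers | Lost | Observed prevalence |
|---|---|---|---|---|
| 0.5% | 10% | 2 | 0.2 | 0.45% |
| 1% | 25% | 4 | 1.0 | 0.75% |
| 2% | 25% | 8 | 2.0 | 1.51% |
| 2% | 50% | 8 | 4.0 | 1.01% |
| 3% | 50% | 12 | 6.0 | 1.52% |

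The range is 0.2 to 6 patients, which in whole patients runs from none to 6 of 400.

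**5. Against sampling error.** The exact 95% interval for 8/400 (2%) is 0.9% to 3.9%, and for 4/400 (1%) it is 0.3% to 2.5%. SAP 7.3 reports prevalence separately by disease, so the intervals are wider still: 4/200 gives 0.6% to 5.0%. A fall from 2% to about 1% lies within these intervals.

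**The case against.** The strongest reply is that the clause is either ordinary or empty. If the two questionnaires exist, as protocol sections 8 and 9.2 say, excluding people who cannot complete them is normal practice, and the fault is only that the instruments are unnamed and unanalysed. If the text is a remnant, sites have no form against which to judge anyone, and the clause should exclude few or none. This is fair, and it means that the documents show an inconsistency and a possible loss, not a demonstrated selection bias. It does not justify keeping the clause, since in the first case an uncompleted form can be recorded as missing, and in the second the clause does nothing useful.

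Other points on that side stand:

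- Written consent already removes many of the patients concerned, particularly those with dementia. Only patients who can consent in writing but cannot complete a form are at issue.
- Both the prevalence and the loss fraction are assumptions.
- Investigator judgement also governs the consent part, so the change does not remove discretion from recruitment.
- Being recorded as uneducated is a schooling level and does not show inability to complete a form.

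One point stands in part. Symptoms and well-being may be taken directly from patients, so understanding questions has some relevance to data quality. But the chart takes priority, and answering a clinician at a visit is a different test from filling in a form.

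**Conclusion.** The point holds as a low-cost improvement. An exclusion tied to questionnaires that no objective, variable or analysis uses can remove consenting patients because of co-morbidities under study. The effects that can be argued from the documents are some downward pressure on the reported prevalence of three conditions and a restriction of their carriers to the less impaired. The number lost cannot be derived from the documents. It is about 0 to 6 of 400 if 0.5% to 3% carry such a condition and 10% to 50% of those are turned away for the form alone, and the consent requirement makes the low end more likely.

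Two stronger readings are tempting and unsupported. A reader might infer that the primary odds ratios are biased in a known direction. Selection on exposure alone does not imply that: exclusion would also have to relate to response, and nothing in the documents says it does. With carriers this few, those odds ratios would be imprecise with or without the clause. A reader might also infer that the questionnaires were abandoned and that all mention of them should simply go. The unused abbreviations are compatible with that, but sections 8 and 9.2 plan collection and data entry, so the sponsor's intention is open.

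**What to change.** 1. In protocol 6.3.3 and SAP 3.8, delete the words about understanding and filling in the questionnaires, so that only inability to give written informed consent remains.
2. If forms are collected, record an uncompleted one as missing and keep the patient.
3. Reconcile protocol sections 2, 8 and 9.2 with section 6.4.4 and the SAP. Either remove the questionnaire text and the unused abbreviations, or name the two instruments and give them an objective, a place among the variables and an analysis.
4. If recruitment has already taken place, report how many patients were excluded under this part of the criterion.

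The cost is wording in two documents. The sample size does not change. The one downside is some missing forms if the instruments are in fact collected, and no planned analysis uses them.

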#### 6.3.4. Discontinuation criteria

As it is a retrospective study, there is no possibility of early termination, hence no discontinuation criteria are considered.

#### 6.3.5. Informed consent

Following the current local regulations, patients will be informed on study objective and methodology through a patient's information sheet (appendix 1) and will also have to give written informed consent before data collection begins (appendix 2).

### 6.4. Study procedure

#### 6.4.1. Study visits

The study will consist of only one visit in which investigators will inform patients about the study objective and methodology and the possibility to take part of it. All data will be collected during the study visit or retrospectively from patients' clinical chart after giving written informed consent. More detail on data collection is given on sections 6.4.3, 6.4.4 and 6.4.5.

#### 6.4.2. Study site monitoring

Regular fortnightly phone calls will be made by study monitors in order to check inclusion status, solve any potential recruitment issues, check data plausibility etc.

As the CRFs will be electronic, filters in the eCRF design may limit the number of queries. Nevertheless, study monitors will check the entered data and deal with any possible queries which may arise in relation with the core data set. If electronic queries are subsequently generated, these will be resolved with physicians by study monitors before completion and validation of the database. The corrections to data will be included in the eCRF either by the investigators or the study monitors. Any correction to data will be recorded in the system together with the automatic identification of the person who performed it and the corresponding date (audit trail). Ongoing eCRF review will be done by the CRO during the study field work.

#### 6.4.3. Data collection

25 gastroenterology centers (one investigator per center) from all around Spain will participate in the study. In order to achieve the minimum sample, each gastroenterology specialist will have 4 months to include approximately 8 UC and 8 CD consecutive patients that fulfill the inclusion/exclusion criteria specified on sections 6.3.2 and 6.3.3. Investigators will inform patients about the study objectives and

methodology and patients will have to give written informed consent before inclusion in the study as specified on section 6.3.5.

Investigators will collect sociodemographic and clinical data from patients' records specified on section 6.4.3 and will introduce it in the eCRF.

#### 6.4.4. Study variables

The following **sociodemographic variables** will be collected from patients' medical records or directly from patients during the study visit, straight after their inclusion in the study:

- Age
- Gender
- Race (caucasian, asiatic, latin, black, other)
- Level of education (uneducated, primary education, secondary education, university education)
- Working status (student, self-employed, employed by other, retired, housework, unemployed, temporarily unable to work, permanently unable to work, other)
- Smoking habits (non-smoker, ex-smoker, smoker, number of cigarettes per day)
- Alcohol intake (units per week).

The following **clinical variables** will be collected from patients' medical records (when available) or directly from patients during the study visit, straight after their inclusion in the study:

- Date of diagnosis (UD or CD).
- Disease activity at the beginning of the reference period and at the study visit through collection of the following variables:
  - For UC patients:
    - Partial Mayo Score (PMS) (9 point scale that excludes the endoscopic appearance of the mucosa)
    - General disease activity:
      - Mild: up to four bloody stools daily and no systemic toxicity
      - Moderate: four to six bloody stools daily and minimal toxicity
      - Severe: more than six bloody stools daily and signs of toxicity, such as fever, tachycardia, anaemia, raised erythrocyte sedimentation rate.
      - Fulminant: More than ten bloody stools daily, continuous bleeding, anaemia requiring blood transfusion, abdominal tenderness and colonic dilatation on plain abdominal radiographs.
    - Disease anatomic extent: proctitis, left-sided colitis or pancolitis.
    - Endoscopy findings:

- Normal or inactive disease
- Mild disease (erythema, decreased vascular pattern, mild friability)
- Moderate disease (marked erythema, lack of vascular pattern, friability erosions)
- Severe disease (spontaneous bleeding, ulceration).
- For CD patients:
  - Harvey-Bradshaw Index (HBI) (a simplified version of CDAI)
  - General disease activity:
    - Mild to moderate: ambulatory patients able to tolerate oral alimentation without manifestations of dehydration, toxicity, abdominal tenderness, painful mass, obstruction or >10% weight loss.
    - Moderate to severe: failure to respond to treatment for mild disease, more prominent symptoms of fever, weight loss, abdominal pain or tenderness, intermittent nausea and vomiting without obstruction, or significant anemia.
    - Severe to fulminant: persisting symptoms on corticosteroids, high fevers, persistent vomiting, evidence of intestinal obstruction, rebound tenderness, cachexia, or evidence of abscess.
  - Disease behaviour: non-stricting and non-penetrating, stricturing and penetrating (fistulas and abscesses),
  - Disease location: terminal ileum.
- For CD and UC patients:
  - Stool frequency (normal number for this patient, 1-2 stools more than normal, 3-4 more stools than normal, 5 or more stools than normal)
  - Rectal bleeding (no blood seen, streaks of blood with stool less than half the time, obvious blood with stool most of the time, blood alone passes)
  - Urgency (hurry, immediately, incontinence)
  - Nocturnal stools (yes/no)
  - Need for antidiarrheal drugs (yes/no)
  - Constipation (yes/no)
  - Abdominal tenderness (none, mild and localized, mild to moderate and diffuse, severe or rebound)
  - Abdominal pain or cramping (none, mild, moderate, severe)
  - Anorexia (yes/no)
  - Nausea (yes/no)
  - Vomiting (yes/no)
  - Fever (yes/no)
  - Appetite loss
  - Weight loss (yes/no)
  - Fatigue (yes/no)
  - Night sweats (yes/no)

- Stunted growth (yes/no)
- Primary amenorrhoea (yes/no)
- General well-being (generally poor, fair, poor, terrible)
- Physician's global assessment (normal or quiescent disease severity, mild disease activity, moderate disease activity, severe disease activity)
- Other complications: severe profuse bleeding, massive bleeding due to ulceration, presence of stomach or duodenum ulceration, intestinal perforation, intraabdominal abscesses, stenosis, obstruction, fistulas, megacolon, others.
- Extraintestinal manifestations in UC and CD patients to be chosen from the following list according to ECCO guidelines:
  - Arthropathy and arthritis
  - Metabolic bone disease
  - Eye disease
  - Oral, aural and nasal disease
  - Skin disease
  - Hepato-pancreato-biliary disease
  - Neurological disease
  - Cardiovascular manifestations of IBD
  - Pulmonary manifestations of IBD
- Urogenital manifestations of IBDComorbidities in UC and CD patients (defined as the coexistence of another medical condition alongside IBD, and does not imply causation) at the time of diagnosis and at the study visit, will be listed according to chosen according to the Charlson index:

Comorbidity Component	Score
Myocardial Infarction	1
Congestive Heart Failure	1
Peripheral Vascular Disease	1
Cerebrovascular Disease	1
Dementia	1
Chronic Obstructive Pulmonary Disease	1
Connective Tissue Disease	1
Peptic Ulcer Disease	1
Diabetes Mellitus	1 (mild), 2 (moderate- severe)
Moderate-Severe      Chronic      Kidney Disease	2
Hemiplegic	2
Leukemia	2
Malignant Lymphoma	2
Solid Tumor	2 (tumor), 6 (if metastasis)
Liver Disease	1 (mild), 3 (moderate-severe)
Acquired immunodeficiency syndrome (AIDS)	6

- Biological treatment/s for UC or CD followed during the reference period:
  - Starting date
  - Posology
  - Intensification of biological treatment: date and type of intensification
  - Continuing with the treatment
  - Date and reason for discontinuation, if applicable
  - New biological treatment prescribed after discontinuation, starting date, posology, continuing with the treatment, date and reason for discontinuation.
- Concomitant treatment with corticosteroids (e.g. prednisone, hydrocortisone, betamethasone, methylprednisolone, etc,) or immunosuppressives (e.g. Ciclosporin, Methotrexate, etc) during induction phase
  - Starting date, number of cycles

Other treatments followed before the reference period to be chosen from the following list:

- Aminosalicylates (e.g. mesalazine, Sulfasalazine, 5-ASA, etc), oral, enema, suppository.
- Corticosteroids (e.g. prednisone, hydrocortisone, betamethasone, methylprednisolone, etc), oral, enema, suppository.
- Thiopurines (e.g. azathioprine, mercaptopurine, etc).
- Immunosuppressives (e.g. Ciclosporin, Methotrexate, etc).
- Anti-diarrheal drugs.
- Pain medications.
- Antidepressants.
- Antibiotics.
- Use of alternative medicine (e.g. acupuncture, relaxation therapy, Qigong, herbal therapy, etc).
- Other (specify)

- Other treatments followed during the reference period to be chosen from the following list:
  - Aminosalicylates (e.g. mesalazine, Sulfasalazine, 5-ASA, etc), oral, enema, suppository.
  - Corticosteroids (e.g. prednisone, hydrocortisone, betamethasone, methylprednisolone, etc), oral, enema, suppository. Number of cycles
  - Thiopurines (e.g. azathioprine, mercaptopurine, etc).
  - Immunosuppressives (e.g. Ciclosporin, Methotrexate, etc).
  - Anti-diarrheal drugs.
  - Pain medications.

- Antidepressants.
- Antibiotics.
- Use of alternative medicine (e.g. acupuncture, relaxation therapy, Qigong, herbal therapy, etc).
- Other (specify)

All patients' data will be handled in a manner that preserves confidentiality.

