#### **3.3. Study code**

Vedolizumab-5016 (MACS-2015-101162)

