## 6. Methodology

### 6.1. Study design

In order to meet the objectives of the present study, a retrospective, non-interventional, multicentre observational study including 25 gastroenterology sites from all around Spain has been designed. Participating investigators will be gastroenterologists and will include consecutive patients diagnosed with UC or CD that started treatment with biologics between June 2011 and June 2013, after giving written informed consent. The study will consist of one only visit in which investigators will collect patients' sociodemographic (age, gender, race, level of education, smoking habits alcohol intake) and clinical (concomitant diseases, date of diagnosis, previous treatment, current treatment, disease activity when starting treatment with biologics and at the study visit, current situation in terms of treatment with biologics) data from medical charts or directly from patients (in case of discrepancy, the information coming from medical charts will be preferable). Time since patients started biological treatment until study visit or until lack of treatment response or until treatment change will constitute the reference period for the study. In order to fulfill current legislations regarding non-interventional studies, investigators will commit to follow usual clinical practice.

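### The source rule lets the baseline HBI or PMS come from patient recall when the chart is silent, against the protocol's own traceability rule; this bears mainly on loss of response and baseline severity

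*Protocol*

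**What the plan says.** Protocol 6.4.4 puts one source rule in front of the whole list of clinical variables: "medical records (when available) or directly from patients during the study visit". An early item in that list is "Disease activity at the beginning of the reference period and at the study visit through collection of the following variables", and the entries beneath it include PMS for UC, HBI for CD and a general activity grade for each disease.

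Protocol 6.1 names the same two sources and ranks them only where they disagree: "in case of discrepancy, the information coming from medical charts will be preferable".

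Protocol 9.2 points the other way: "All the information introduced in the eCRF will need to be traceable from original medical charts". The same section says that there will be no on-site monitoring.

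The baseline moment is fixed by Protocol 6.3.2: "Patients naive to biologics that started treatment with biologics between June 2011 and June 2013". Protocol 6.4.5 builds the outcome on that baseline: a CD non-responder is a patient "not achieving a reduction in HBI of at least 2 points from baseline for CD", with a matching 2-point rule on PMS for UC. Where the index is unavailable, physician criteria decide. SAP 7.1 repeats this, and SAP 7.3 uses baseline HBI and PMS to split patients into severe and non-severe.

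The SAP adds no rule on the source of the baseline index, no flag for recalled values and no sensitivity analysis by source.

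**The concern.** Baseline is one half of the change score. A patient asked at the visit about stools, pain and well-being at the first infusion or injection already knows whether the drug worked, and so does the investigator entering the answer. Error in that half moves patients across the 2-point cut.

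If the error is unrelated to comorbidity, a real association is diluted. If chart completeness or recall differs between patients with and without comorbidity, an association can appear where none exists. The second case matters more, because comorbidity is the exposure under study.

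The preference for the chart does not help when the chart is empty, since there is then no discrepancy to resolve. As no source field is listed, recalled values could not be identified or set aside at analysis.

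**Working it through.** **1. The plan's own figure.** Protocol 7.1 assumes 10 events per variable, 10 variables and 50% non-response: N = 10 × 10 / 0.50 = 200 per disease. This reproduces, and the present point does not change it.

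**2. Gap between baseline and visit.** The visit date is not stated. The study code carries 2015, and protocol reference 33 is dated 2016. If the visit is no earlier than the start of 2016, the gap is at least about 2.5 years for a June 2013 starter and 4.5 years for a June 2011 starter. This is an inference.

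**3. Which outcomes are reached.**

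| Outcome | Index values needed | Listed in Protocol 6.4.4? |
|---|---|---|
| Primary non-response (10 weeks) | baseline and week 10 | baseline only |
| Loss of response (6 months or later) | baseline and a later value | baseline and study visit |
| Severe / non-severe at baseline | baseline | yes |

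Without a listed week-10 index, primary non-response will mostly fall to physician criteria whatever the source of the baseline. The exposure lies in the second and third rows.

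**4. Misclassification among recalled patients (assumed error).** Observed fall = true fall d + error, where the error is N(0, SD) rounded to whole points; scale limits are ignored. P(observed fall < 2) = Φ((1.5 − d)/SD).

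- d = 2: Φ(−0.5/1) = 31% at SD 1; Φ(−0.5/2) = 40% at SD 2.
- d = 3: Φ(−1.5/1) = 7% at SD 1; Φ(−1.5/2) = 23% at SD 2.

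By symmetry, the same shares of true falls of 1 and 0 are counted as responses. These percentages apply only to patients whose baseline is recalled.

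**5. Differential recall under a true null (assumed).** True falls follow a discretised normal with mean 1.5 or 2 and SD 2 to 3, which gives true response of 50-60%. A share f of comorbid patients has a recalled baseline that is 1 point too high; the other patients have no such shift.

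- p0 = 1 − Φ((1.5 − mean)/SD)
- p1 = 1 − Φ((0.5 − mean)/SD)
- Observed OR for response = odds((1 − f)p0 + f·p1) / odds(p0)

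Example with mean 1.5, SD 2, f = 0.10: p0 = 0.500 and p1 = 0.691. The mixture is 0.9 × 0.500 + 0.1 × 0.691 = 0.519, and OR = (0.519/0.481)/1 = 1.08.

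| Share of comorbid patients recalled | OR seen when the truth is 1.0 |
|---|---|
| 10% | 1.05-1.08 |
| 20% | 1.11-1.17 |
| 50% | 1.3-1.5 |
| 100% | 1.7-2.3 |

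A shift in the opposite direction would push the OR below 1.

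**6. Non-differential recall (assumed).** Let recalled outcomes have sensitivity and specificity of 0.7 and the rest be correct, with 50% non-response in the unexposed. Overall sensitivity and specificity are then (1 − f) + 0.7f, where f is now the recalled share of all patients. A true OR of 2.0 is seen as 1.91, 1.75 or 1.61 at f = 10%, 30% or 50%.

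**The case against.** The strongest reply is that the lead-in in Protocol 6.4.4 is a generic sentence about two sources. It also covers endoscopy findings, posology and the physician's global assessment, most of which a patient cannot supply. Section 6.4.3 speaks of collecting clinical data from records, and 9.2, if enforced, would bar any value without a chart source. On that view recall of the baseline index was never intended.

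Part of this stands. The documents do not show that the plan adopts recall as its baseline method: the chart is the first source, and how often it would be silent is unknown. But HBI and PMS are largely symptom scores that a patient could be asked about. The wording allows it, and 9.2 contradicts that wording without resolving it. Remote monitoring gives little means of enforcing traceability.

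Three stronger readings are tempting and should be resisted.

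- A reader might infer that both primary outcomes are compromised. With no week-10 index listed, primary non-response is largely outside this mechanism.
- A reader might infer that a recalled index shuts off the physician fallback. Protocol 6.4.5 and SAP 7.1 do not say whether a recalled index counts as available; the order of the two is simply not set.
- A reader might infer a spurious odds ratio near 2. That requires every comorbid patient's baseline to be recalled, each 1 point too high, with no such shift in the others.

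**Conclusion.** The point holds as a conflict between Protocol 6.4.4 (with 6.1) and 9.2 over the source of baseline disease activity. It should be fixed, but it does not by itself undermine the primary analysis.

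Its reach is the change to the study visit, hence loss of response, and the severe/non-severe split in SAP 7.3. Its size cannot be taken from the documents, which give neither the share recalled, nor recall accuracy, nor any link between recall and comorbidity. If recall is occasional (10-20% of comorbid patients), the assumed 1-point differential shift produces an odds ratio of 1.05-1.17 under the null, which is small. At one half it reaches 1.3-1.5, enough to be mistaken for a modest comorbidity effect. The 100% figure marks the extreme and is not an expected value. That the gap runs to years rests on the dates in the study code and reference list.

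**What to change.** - In Protocol 6.1 and 6.4.4, accept baseline HBI, PMS and general disease activity only from chart entries dated at or before the first biologic dose, within a stated look-back window.
- Where no such entry exists, record the index as not available and apply the existing physician-criteria route, based on contemporaneous chart notes. Without that condition, a judgement made at the visit would carry the same hindsight.
- Limit direct patient report to sociodemographic items and current status at the visit. This brings 6.1 and 6.4.4 into line with 9.2.
- Add an eCRF field for the source and date of the baseline index.
- In the SAP, add a sensitivity analysis restricted to chart-documented indexes.

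The cost is protocol and SAP wording and one eCRF field. More patients will be classified by physician criteria, and some will have no baseline severity class. The restricted analysis will also be smaller: if 70% of charts hold an index (assumed), 200 patients give 200 × 0.70 × 0.50 = 70 events, enough for 7 variables at 10 events each; at 90% and 50% the events are 90 and 50.
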